possible alcohol dependence, using an AUDIT-C score of greater than 8. Our electronic data collection instruments will flag these participants in real-time and alert the interviewer to take action. In this case, we will provide simple advice to help participants cut down slowly on their alcohol use and avoid the negative effects of alcohol withdrawal. For example, participants will be advised: "If you are a heavy drinker, we advise you to gradually reduce your alcohol consumption. We advise that you do not stop drinking suddenly because you may feel alcohol withdrawal symptoms that may seriously affect your health." We will continue with study activities but will have procedures in place to refer patients to several private alcohol and substance use referral centers/services in the local area (SANCA, LifeLine, and SADAG). At any point in the study, participants who request or ask about services to help them with their alcohol dependency will be referred to such services. If significant alcohol problems are encountered during the couples' MI sessions or other intervention activities, study participants will be encouraged to discuss these problems with their health care providers and will be referred to alcohol and substance use services in the community.

Procedures for handling severe depression and suicidality: If a participant shows signs of severe depression (e.g., score ≥ 20 on the PHQ-9 scale) or suicidality (e.g., indication on PHQ item 9) during the study assessments or intervention sessions, study staff will follow an established protocol to assess risk and make the appropriate referrals and linkages into services. In the case of suicidality, staff will be trained on how to conduct a suicide risk assessment including how to differentiate between potential suicidal ideation and non-suicidal ideation. In the case of suicidal ideation, staff will assess past and current suicidal episodes and screen for other risk and protective factors to determine the appropriate safety plan. Referrals and linkage into services will be made in consultation with the broader HSRC clinical and community outreach teams using internal procedures for handling cases of distress and poor mental health.

COVID-19 safety management plan: To protect study participants, their families and research staff from the risk and spread of COVID-19, the study will adhere to all Kwa-Zulu Natal Department of Health directives aimed at mitigating the spread of COVID-19. We will inform research participants of requirements to undergo COVID-19 screening and reporting of screening results to the local public health authorities whenever the results may point at a possible infection with the disease, for their benefit. We will also provide participants and staff with 3 ply face masks, avail hand washing stations at the study sites, and provide hand sanitizers. We will pre-screen participants before physical contact, check temperature and observe social distancing requirement of 1.5 meters during face-to-face interaction with participants. We will inform the participants of the measures that we will be taking during any form of face-to-face contact. We will also have daily mandatory screening for staff who are making contact with participants, and only those without any COVID-19 symptoms will be allowed to make contact with participants. The staff will also disinfect furniture and sanitize their hands after every contact with a participant. Finally, we will select a large conference room with good ventilation (open windows and fans) to further reduce risk of transmission for COVID-19.

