Few couple-based MI approaches have been developed for alcohol use, particularly in the African context. In the US, there is evidence that couple-based MI is feasible, acceptable, scalable, and efficacious at reducing substance use.[9, 18-20] In studies with individuals, daily monitoring of drinking levels, when paired with MI, has a greater effect on drinking than MI alone[15-17] and we hypothesize that monitoring may have additional benefits with couples. Although primary partners are generally aware of a drinker’s alcohol use, they have inaccurate knowledge of drinking amounts and frequency, in part, because drinking often occurs in gender-segregated spaces in SSA. Accurate knowledge of drinking levels in real-time is critical to trigger couple communication, and timely and tailored social support. Mobile breathalyzers have been shown to be a feasible and acceptable strategy for self-monitoring alcohol use in studies with individuals[21-23] and new products have been developed for dyads that share blood alcohol content (BAC) levels with support partners via a mobile app. Our scientific premise is that mobile breathalyzers to provide real-time feedback and support can be synergistic with a couple-based MI approach that fosters couple communication and problem-solving skills to effectively engage with the breathalyzers and work together to reduce alcohol use. We hypothesize that this combination will have a greater effect on drinking reductions than couple-based MI alone.

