4.0 Intervention Description

The two intervention arms consist of standalone MI (arm 2) and MI *Plus* (arm 3), which consists of MI sessions in arm 2 plus use of the mobile breathalyzer and app for two months. Both intervention arms are conducted with the couple as a unit.

MI *Plus* will consist of: 1) manualized MI sessions with couples and a counselor; 2) handheld breathalyzer with accompanying mobile app to deliver real-time feedback on drinkers' BAC levels to both partners. BAC data collected will be also used to provide personalized feedback based on summarized displays (e.g., calendar) of BAC levels in the MI sessions.

MI Sessions: We will aim for around 3 in-person sessions over a 60-day period with each session lasting 60-75 minutes – consistent with the format used in the Couples Health Project. We will administer MI sessions that are structured and manualized, as a roadmap for moving through content. MI is a collaborative process between a counselor and client, aimed at exploring and resolving ambivalence towards changing a behavior. Our approach will center around four MI processes (engagement, focusing, evoking, and planning)[30] and a fifth process around relationship quality based on co-I [name]' MI framework for couples[19, 20]. [name] recently published a paper using qualitative data from a couple-based MI intervention that supports the necessity of including relationship quality as a fifth MI process when working with couples.[31] An exploration of dyadic strengths is necessary to support couples with divergent views in the resolution of interpersonal ambivalence and the development of shared goal. [name] developed structured activities for exploring couples' shared goals and a lexicon of counselor skills that are effective in responding to dyadic ambivalence and achieving accommodation.[20]

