Outline of MI Sessions: The first session will occur within two weeks after baseline and the two subsequent sessions will be delivered at 30 and 60 days after couples have used the breathalyzer app. In the first session, the counselor will establish rapport and draw out the couples' communication strengths and weaknesses. The counselor will review baseline alcohol levels using this as a starting point to evoke change talk. The session ends with the creation of a goal to reduce alcohol use. Session 2 will review the BAC data (or self-reported alcohol use if in the non-breathalyzer arm) from the past 30 days using a calendar approach, a check-in on goals set in Session 1, and a review of communication successes and challenges. The session ends with the creation of a behavioral goal for the next session. Session 3 begins with a review of BAC data (or self-reported alcohol use if in the non-breathalyzer arm) from the past 30 days using a calendar approach, a check-in on goals set in Session 2, and ends with a discussion of long-term goals and related planning. If both partners are heavy drinkers, then couples will develop goals in each session for both partners.

Mobile Breathalyzer for Couples: We will use BACtrack View®, which consists of a handheld commercial-grade breathalyzer and mobile app. To avoid disruptions in cellular service by having to manually purchase data, we will automatically replenish participants' data when running low. To reach those who could greatly benefit from the intervention and to avoid

Couple-Based Motivational Interviewing with Mobile Breathalyzers to Reduce Alcohol Use in South Africa

widening the digital divide, we will provide phones to participants who do not have compatible smartphones.

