5.9 Control condition. Participants will receive the Usual Care (UC) defined by the South African national 2019 ART Clinical Guidelines (updated in March 2020). The harms of alcohol use are briefly discussed during the morning health talks in the waiting rooms of HIV clinics. HIV clients are advised that alcohol intake should be reduced to <2 standard drinkers/day for men and <1 for women for 5 out of 7 days per week. After randomization, couples in the control arm will receive brief alcohol counseling modeled off WHO guidelines and [name] intervention in Malawi, which uses participants' baseline AUDIT scores for messaging around alcohol reduction and lasts 5-10 minutes. In selecting the control, we chose to balance our ethical obligation to provide basic health information on alcohol use (minimal in this setting), while maximizing the generalizability of our findings to inform a future RCT, which will employ a UC control group. Clinical trial experts recommend the UC condition over other designs such as a time-and-attention control (TAC) when the long-term goal is to inform implementation science and scale-up. Our long-term goal will be to test the effectiveness of a scalable alcohol intervention. Moreover, because TAC designs have an active but different intervention, there is the risk of positively-biased intervention results because the comparison arm can distract participants from making reductions in alcohol use they would have otherwise made.

5.10 Procedures for mobile breathalyzers with couples in MI *Plus* arm. Drinkers will be provided with handheld breathalyzers and both partners will receive access to the breathalyzer results. Drinkers will receive SMS requests to take a breathalyzer test twice per day (e.g., in the morning at 11 am and in the evening at 8 pm). After the drinker completes each breathalyzer test, the partner receives a notification that the drinker completed a test and can view the test results. Partners will receive a unique login username and password linked to their study ID. [name] and the research manager(s) will facilitate a 1-2 hour training for couples how to use the breathalyzers/phones (e.g., charging, Wi-Fi, Bluetooth), complete breathalyzer tests, app functionality, trouble-shooting issues, and technical support. Couples will be instructed to use the breathalyzers for a 60-day period. Assessments at 60 days will allow us to assess the effects on alcohol use immediately following the 60-day intervention period.

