A technology navigator will monitor daily compliance and check-in with participants to assist with login credentials, lost or damaged devices, cellular connectivity, difficulties using the phones or breathalyzers, and intentional non-use of the breathalyzers—with close monitoring during the first week. Navigators will monitor for safety issues and IPV (interpersonal violence) during routine check-ins and will provide assistance should a safety/IPV issue arise.

5.11 Survey assessments. Assessment visits will be held in community-based locations such as youth centers or in our team's mobile caravans used in other couples' studies. To minimize loss-

Couple-Based Motivational Interviewing with Mobile Breathalyzers to Reduce Alcohol Use in South Africa

to-follow-up, we will administer follow-up surveys over the phone in the case that a participant moves out of the area or is unavailable for an extended period of time. For the pilot study, surveys will be administered at baseline and 2-months (after receiving all MI sessions and/or using the breathalyzers for 60 days), and 6-months post-intervention initiation. Measures collected will be the same across visits with the exception of time-invariant variables such as demographics (collected at baseline only). All measures will be pre-tested, tailored for South Africa, and translated to *isiZulu* and back-translated to English. See Appendix with full survey instrument. Survey assessments will be interviewer-administered on tablet devices using REDCap mobile, last around 90 minutes, and uploaded to a secure web-based storage system. Partners will be assessed separately, but simultaneously, in private interview rooms.

	Domain	Measure (alphas noted are from prior studies with couples)
Primary outcomes (future trial)	Alcohol use	Number of drinking days in past 21, assessed using the three-week timeline follow-back method (TLFB) confirmed with the PEth biomarker.[32] AUDIT-C positive (score of ≥ 4 for men and ≥ 4 for women) and/or PEth positive (≥ 35 ng/ml).[33, 34]

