The consent form will include specific language regarding the confidentiality of the partner's study data: "Please be aware that you will not be told any information that your partner says in his or her interview. This includes any information your partner might say about his or her health, even if we think you do not know this information. Likewise, no information you say in your interview will be told to your partner, even if we think your partner might not know this information." Interviewers will be trained to ensure that participants understand this condition during the informed consent process, including information about the confidentiality of their own

Couple-Based Motivational Interviewing with Mobile Breathalyzers to Reduce Alcohol Use in South Africa

and their partner's data. As mentioned above, systematically providing this information will eliminate partner's surmising that it is being provided due to information disclosed during the interview. It is possible that partners might ask each other about their responses to certain questions or issues discussed. Interviewers will be trained to discuss with participants ways of coping with this situation.

Loss of privacy. We will screen and interview couples in private locations and will take additional measures to protect respondents' HIV+ status. Although most activities will take place in the HIV clinics or other central community-based location, it will be important that interviewers maintain respondents' privacy if visiting the communities of respondents. To protect individuals' privacy, we will utilize language such as "Healthy Living" rather than referring to HIV or alcohol use when discussing the study.

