Couple tension, conflict, and/or violence, and coercion. It will be communicated in the consent form that while study staff members will not reveal participant information to their partner, it is possible that their partners might ask them about their responses to certain questions or issues they discussed. Interviewers will be trained to discuss with participants' ways of coping with this situation if the participant expresses concern or distress about this matter during consent, the administration of the survey, or after it is completed.

Although we have not had problems in the past in South Africa with participants reporting coercion, staff members will be trained to be sensitive to the possibility that one member of the couple was pressured or coerced by the other partner to participate in the study. Questions may be posed such as "Did you come here freely?" or "Will something bad happen to you if you say

Couple-Based Motivational Interviewing with Mobile Breathalyzers to Reduce Alcohol Use in South Africa

no?" Should the staff member have this suspicion, s/he will be trained to immediately terminate the survey or session and provide the participant with appropriate referrals and the study incentive. Any data collected will be destroyed. The staff member will also be trained to offer the participant the opportunity to remain in the interview room for the appropriate amount of time that it would have taken to complete the survey or interview so that the study partner would not be alerted to the fact that the interview was terminated. If necessary, back-up staff members who are clinicians can be contacted to assess the appropriate immediate steps, should intervention be needed. Should evidence of coercion/violence arise in the intervention sessions, assessment visits, or exit interviews, the counselor will provide the appropriate clinical intervention regarding participation of the couple, including assessing the level of safety and whether immediate medical/psychological attention is needed, and/or provide community referrals. Depending on the situation, procedures as described above will be followed in terms of determining next appropriate steps.

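### The consent wording promises that nothing said in the private interview reaches the partner, yet Session 1 in arms 2 and 3 reviews baseline alcohol levels with the couple together

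*Combined protocol and SAP*

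**What the plan says.** **The promise.** Section 8.3 (loss of confidentiality) gives the language the consent form must carry: "no information you say in your interview will be told to your partner, even if we think your partner might not know this information". Interviewers are to be trained to make sure participants understand it. The later part of 8.3 on couple conflict and coercion has the consent form repeat the assurance in wider terms: "while study staff members will not reveal participant information to their partner". Neither statement has an exception.

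**How drinking is asked.** Section 5.11 says of the surveys: "Partners will be assessed separately, but simultaneously, in private interview rooms". The alcohol row of its measures table covers drinking days ("Number of drinking days in past 21, assessed using the three-week timeline follow-back method (TLFB) confirmed with the PEth biomarker") and AUDIT-C.

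**How the answers are used in arms 2 and 3.** Section 4.0 says "Both intervention arms are conducted with the couple as a unit". Its outline of Session 1 starts with rapport and the couple's communication, and continues: "The counselor will review baseline alcohol levels using this as a starting point to evoke change talk".

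**Control arm.** Section 5.9 gives couples 5-10 minutes of brief counselling, modeled partly on an earlier intervention in Malawi, which "uses participants' baseline AUDIT scores for messaging around alcohol reduction".

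**The concern.** A drinker answers alcohol questions apart from the partner, under an assurance that staff will pass nothing on. Within two weeks a counselor reviews that drinker's baseline level in front of the same partner. If both instructions are followed, the assurance fails in an ordinary, planned session.

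The protocol itself says why this matters. Section 8.3 names disclosure of alcohol problems, and questioning by family about drinking, among the harms of lost confidentiality. It lists conflict and violence between partners as a study risk. Couples reporting mild or moderate partner violence may enrol. The consent wording is therefore a safeguard on which participants are meant to rely.

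**Working it through.** No formula applies and the plan gives no figure to reproduce. The check is whether the sections can all be followed at once.

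1. **Is the promise limited?** The fixed wording in 8.3 has no carve-out, and it expressly covers facts the partner may not know. The one qualification found elsewhere, in 8.3.1, lets interviewers compare partners' answers when the study requires it, for example to confirm eligibility. That is not permission to tell a partner the answers.

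2. **Where can a baseline alcohol level come from?** The candidates in the protocol are:
   - PEth: section 5.13 describes blood collection for PEth at the two-month visit, and 3.1 refers to follow-up visits. No baseline PEth is described.
   - Breathalyzer: section 4.0 brings BAC data in at Sessions 2 and 3, after couples have used the device. Arm 2 has no device.
   - Interview: AUDIT-C at screening (3.1), and the alcohol measures in the baseline survey (5.11).

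   Only the interview remains. Section 3.2 places consent after screening, so a screening AUDIT-C is given before the consent wording is read. The wider restatement in 8.3, that staff will not reveal participant information, would still cover it.

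3. **Is the partner present when it is reviewed?** Yes in arms 2 and 3, by section 4.0. The counselor is the one who carries out the review.

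4. **Can the review tell the partner anything new?** The introduction says partners generally know of the drinking, but "they have inaccurate knowledge of drinking amounts and frequency". The fact of drinking is unlikely to be news. The level may be, and the level is what Session 1 reviews.

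5. **How many couples?** Section 2.5 plans 30 couples per arm, so 2 x 30 = 60 of the target 90. Section 5.7 plans to randomize around 120. With equal allocation that is 2 x (120 / 3) = 80 couples, before losses. Both are upper limits, because only couples who attend Session 1 are exposed.

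6. **Does the control arm show the same conflict?** Section 5.9 has couples receive the counselling. It does not say that both partners are in the room or that a score is spoken. The clause about AUDIT scores can also be read as describing the Malawi intervention. The conflict is possible there, but not shown.

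**The case against.** The strongest reply is that the breach is inferred. Section 4.0 does not say that interview records go to the counselor or that a score is read out. Facilitators and interviewers are described separately in 5.4, and no data handover between them is set out. In the non-breathalyzer arm, Sessions 2 and 3 work from self-reported drinking, so the counselor might simply ask the drinker again in Session 1. This may be what is intended, and it is why the alternative fix could be a single sentence. But the sentence on Session 1 has the counselor reviewing baseline levels, and the protocol describes no source for them other than the separate interviews. A reader following the text would use those data.

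A second reply is that the consent form, which was not available for review, may explain the joint discussion. Section 8.2 does promise a detailed account of procedures. If the form does explain it, the form must also carry the wording fixed in 8.3 and would then conflict with itself.

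Three stronger readings are tempting, and the documents do not support them:

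- **All arms are affected.** Section 5.9 does not establish joint delivery or disclosure of scores, so the control couples cannot be counted.
- **Session 1 confronts the couple with the drinking level at the outset.** Rapport and communication come first.
- **The disclosure biases the drinking outcome in favour of the MI arms.** A drinker whose answers surfaced in a session might report less later, but nothing in the documents gives a size for this. Arms 2 and 3 share the same Session 1, so their comparison (H2) has no obvious imbalance from it. Drinking hypotheses are exploratory under 7.3, and drinking days are to be confirmed with PEth. Changing the consent wording would also leave the joint review in place, so it would not cure such a bias.

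**Conclusion.** The point holds for arms 2 and 3. The unconditional assurances in 8.3 and the Session 1 outline in 4.0 cannot both be followed as written, and they must be reconciled. The exposure is up to 60 of the target 90 couples, or about 80 if 120 are randomised equally.

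The conclusion rests on two readings: that baseline alcohol levels come from the separate screening or baseline interview, and that the wording in 8.3 is what participants hear. It does not rest on BAC sharing in arm 3, which is not something said in an interview. It does not touch sample size or error rates. Section 5.9 needs clarifying, but is not shown to be in conflict.

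**What to change.** Reconcile both statements in 8.3 with the Session 1 outline in 4.0, in one of two ways.

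- **Preferred.** Amend the consent wording to say that a participant's baseline alcohol answers may be used in counselling with the partner present, and that other interview answers stay confidential. Use the same text for all arms, before the baseline interview. Align the restatement in the coercion part of 8.3.
- **Alternative.** Keep the promise. State in 4.0 that interview alcohol data are not passed to counselors and that Session 1 uses only what the drinker reports there.

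Under either option, state in 5.9 whether both partners attend the control counselling, whose AUDIT score is used, and whether it is spoken in front of the partner.

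The cost is a short amendment, approval by both ethics bodies, re-translation of the changed consent text and a briefing for interviewers and facilitators. The downside of the preferred option is that some baseline answers may become more guarded. That should fall equally on the arms, because section 5.8 places the baseline assessment before randomisation. The downside of the alternative is that Session 1 loses the recorded baseline as its starting point. For any couple already consented under the present wording, only the alternative keeps the assurance they were given, unless they consent again.
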